11. SELECTION AND WITHDRAWAL OF SUBJECTS

11.1. Subject Inclusion Criteria

No subject will be assigned to treatment until all eligibility criteria have been satisfied. To qualify for the study a subject must:

1. Be able to provide voluntary written informed consent prior to the initiation of any study-specific procedures per the policy of the governing Institutional Review Board (IRB)/Independent Ethics Committee (IEC).
2. Be female and at least 18 years of age at the time of consent.
3. Have evidence of cellulite in 2 bilateral treatment areas (defined as right and left buttocks OR right and left posterolateral thighs) as assessed by the Investigator at the Screening visit, and fulfills the following requirements:
 - a. has a score of 2 (mild), 3 (moderate) or 4 (severe) as reported by the Investigator (CR-PCSS) in 2 treatment areas (two thighs or two buttocks) at the Screening Visit.
 - b. has at least 2 dimples from each treatment area that:
 - are isolated and separated by at least 5 cm from any other dimples.
 - score 2 or 3 on the Hexsel depression scale.
 - have dimple width: length ratio ≥ 0.5 .
4. Be willing to apply sunscreen to the dosing areas before each exposure to the sun while participating in the study (ie, screening through end of study).
5. Be judged to be in good health, based upon the results of a medical history, physical examination, and laboratory profile at screening.
6. Have a negative serum pregnancy test at the Screening Visit and negative urine pregnancy at Day 1 (before injection of study drug), be using an effective contraception method (eg, abstinence, intrauterine device, hormonal [estrogen/progestin] contraceptives, or double barrier control) for at least 1 menstrual cycle prior to study enrollment and through Day 71 ; or be menopausal defined as at least 12 months of amenorrhea in the absence of other biological or physiological causes (as determined by the Investigator), or be postmenopausal for at least 1 year, or be surgically sterile (hysterectomy, bilateral oophorectomy, bilateral tubal ligation).
7. Be willing and able to comply with all protocol required study visits and assessments.

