## **3. STUDY DESIGN AND MEASURES**

### **3.1. Study Design**

This is a Phase 2a, open-label, multicenter, exploratory study to evaluate the safety and effectiveness of different injection techniques of CCH for the treatment of adult women with EFP. This study will be performed at approximately 5 sites in the United States (US).

Subjects having the evidence of cellulite in 2 buttocks or 2 thighs (treatment area) at the Screening Visit will be enrolled if they satisfy the criteria below:

- Have a CR-PCSS score of 2 (mild), 3 (moderate) or 4 (severe) as reported by the Investigator in 2 treatment areas (two thighs or two buttocks)
- Have at least 2 dimples from each treatment area that:
  - are isolated and separated by at least 5 cm from any other dimples

- score 2 or 3 on the Hexsel depression scale
- have dimple width: length ratio  $\geq 0.5$

If both buttocks and both thighs meet entry criteria for a single subject, then the thighs will be treated. No subject will be treated for EFP in both the buttocks and the thighs during this study.

The study will enroll approximately 60 subjects; 30 subjects with 2 eligible buttocks (to be dosed in the buttocks) and 30 subjects with 2 eligible thighs (to be dosed in the thighs). The 30 subjects in each treatment region (buttocks or thighs) will be assigned sequentially to 1 of 5 injection technique treatment arms on Day 1 (ie, 6 subjects per region per treatment arm). No control groups will be employed. Subjects who discontinue from the study will not be replaced.

Subjects who complete the study will participate for approximately 92 days including a 21-day of screening period, a 43-day treatment period and a 28-day follow-up period. Subjects will receive the study injections on Days 1, 22, and 43. Additional scheduled assessments will be performed on Days 4, 8, 15, and 71.

[Table 1](#) below describes the schedule of events and assessments performed during screening, treatment visits, and assessment visits.

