### 3.2. Inclusion Criteria

No subject will be assigned to treatment until all eligibility criteria have been satisfied. To qualify for the study a subject must:

1. Be able to provide voluntary written informed consent prior to the initiation of any study specific procedures per the policy of the governing Institutional Review Board (IRB)/ Independent Ethics Committee (IEC).
2. Be female and at least 18 years of age at the time of consent.
3. Have evidence of cellulite in 2 bilateral treatment areas (defined as right and left buttocks OR right and left posterolateral thighs) as assessed by the Investigator at the Screening visit, and fulfills the following requirements:
  - a. has a score of 2 (mild), 3 (moderate) or 4 (severe) as reported by the Investigator (CR-PCSS) in 2 treatment areas (two thighs or two buttocks) at the Screening Visit.
  - b. has at least 2 dimples from each treatment area that:
    - are isolated and separated by at least 5 cm from any other dimples
    - score 2 or 3 on the Hexsel depression scale
    - have dimple width: length ratio  $\geq 0.5$
4. Be willing to apply sunscreen to the dosing areas before each exposure to the sun while participating in the study (ie, screening through end of study).
5. Be judged to be in good health, based upon the results of a medical history, physical examination, and laboratory profile at screening.
6. Have a negative serum pregnancy test at the Screening Visit and negative urine pregnancy at Day 1 (before injection of study drug), be using an effective contraception method (eg, abstinence, intrauterine device, hormonal [estrogen/progestin] contraceptives, or double barrier control) for at least 1 menstrual cycle prior to study enrollment and through Day 71; or be menopausal defined as at least 12 months of amenorrhea in the absence of other biological or physiological causes (as determined by the Investigator), or be post-menopausal for at least 1 year, or be surgically sterile (hysterectomy, bilateral oophorectomy, bilateral tubal ligation).
7. Be willing and able to comply with all protocol required study visits and assessments.

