### 3.6.2. Blinding and Randomization

This is an open-label study. Subjects will be sequentially assigned to a treatment arm at Day 1.

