## **6.2. Adjustments for Covariates**

Not applicable.

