**Table 12: Derived Variables and Definition**

Variable	Definition
Age Group	<35 years 35 – <45 years 45 – <65 years ≥65 years
Height (cm)	If height is recorded in inches, then height is equal to the recorded value multiplied by 2.54 and then rounded to 1 decimal place.
Weight (kg)	If weight is recorded in pounds, then weight is equal to the recorded value multiplied by 0.454 and then rounded to 1 decimal place.
Body Mass Index (BMI)	BMI will be computed using height and body weight measured at screening as, $BMI (kg/m^2) = Weight (kg) / Height (m)^2$
BMI Group	Underweight (<18.5 kg/m  ) Normal Weight (18.5 – <25.0 kg/m  ) Overweight (25.0 – <30.0 kg/m  ) Obese (≥30.0 kg/m  )
Relative Day	The day of first injection of study drug will be considered as relative day 1
Study Day (for assessment on or after Day 1)	Study Day will be computed as, Date of Assessment – Date of Day 1 + 1
Study Day (for assessment before Day 1)	Study Day will be computed as, Date of Assessment – Date of Day 1
Baseline	Baseline is defined as the last non-missing measurement/assessment prior to the first dose of study drug. For vital signs, the baseline will be the Day 1 pre-dose values. For clinical laboratories this could be the screening value, or it could be an unscheduled lab, if the unscheduled lab is the closest value preceding the first injection.
Change from Baseline	Change from baseline will be derived as, post-baseline visit/time point value – the baseline value.
Last Date in Study	
 
• The date of Day 71 if the subject completes the study
 
• The date of early termination visit if the subject is terminated early from study at a non-scheduled visit
 
• The date of the latest scheduled visit if the subject is terminated early from study at a scheduled visit or lost to follow-up.
 

Age at EFP Symptom Onset	Date of EFP symptoms reported – Date of Birth/365.25. See section 6.4.1.3 for handling of partial or unknown EFP symptom onset dates.
Time Since Last EFP Treatment	Date of most recent EFP treatment – Date of informed consent/365.25. See section 6.4.1.3 for handling of partial or unknown EFP treatment dates.
Baseline CR-PCSS Score	Investigator baseline CR-PCSS scores for each treatment area will be based on the investigator's CR-PCSS evaluation done at the Screening visit.

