### **7.7.1. Improvement in Aesthetic Appearance using 3-D Photographic Images**

#### **7.7.1.1. Analysis of Treatment Region and Area**

The Likert Scale score of improvement in aesthetic appearance from baseline will be analyzed using a linear mixed model with treatment arm, study visit, interaction of treatment arm and study visit as fixed effects. The fixed effect estimates and 95% CIs for interaction effect of treatment arm and study visit will be presented. This model will be fitted using the response for each treatment area (ie, left buttock, right buttock, left thigh, and right thigh) and for the average of left and right of treatment area (ie, average of left buttock and right buttock; average of left thigh and right thigh).

The Likert Scale rating of improvement in aesthetic appearance from baseline will also be summarized using count and percentage by treatment arm and study visit/day (Day 22, 43, and 71) for each treatment area and with mean and SD.

A listing of Likert Scale scores will be provided.

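### The blinded Likert model has no baseline severity term although Screening CR-PCSS is already derived per area; adjusting for it is a cheap gain, mainly in precision

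*SAP*

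**What the plan says.** - **Model.** SAP 7.7.1.1 states that the Likert score "will be analyzed using a linear mixed model with treatment arm, study visit, interaction of treatment arm and study visit as fixed effects". It is fitted to each treatment area and to the left-right average within a region.
- **Covariates.** SAP 6.2, on covariate adjustment, reads "Not applicable". SAP Table 13 drops the protocol's cellulite-dimples term (Protocol 17.5), and no severity term replaces it.
- **Severity range.** Protocol 11.1 and SAP 3.2 admit areas that the investigator scores 2 (mild) to 4 (severe) on the CR-PCSS at Screening.
- **Arm size and assignment.** SAP 3.1 gives the allocation as "ie, 6 subjects per region per treatment arm", and discontinued subjects are not replaced. SAP 3.6.2 states: "Subjects will be sequentially assigned to a treatment arm at Day 1". No stratification by severity is described.
- **Available baseline.** SAP Table 12 defines "Investigator baseline CR-PCSS scores for each treatment area" from the Screening visit. Their only analytic use is the baseline table in SAP 7.3.

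**The concern.** The Likert score is the only efficacy measure stated to be rated blind to arm (Protocol 13.1, SAP 3.8), and it defines the Evaluable Population. It is itself an improvement rating and has no baseline value, so any adjustment for starting severity must use another variable.

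Its levels run from worse to an optimal cosmetic result (SAP Table 5). How far an area can move on that scale plausibly depends on how severe it was at the start. With 6 subjects per arm in a region, mean severity will usually differ between arms. If severity predicts the rating, the unadjusted model leaves that variation in the residual error, and does not correct the arm comparison for the imbalance actually seen. At stake is how precisely and fairly five techniques are compared when each contrast rests on 6 against 6.

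**Working it through.** **1. The plan's own figure.** 2 regions x 5 arms x 6 subjects = 60, as stated. There is no power calculation to reproduce: Protocol 17.1 says none was done and SAP 3.6.1 calls the number empirical. Likert SD, severity mix and severity-Likert correlation are therefore assumptions below. Each calculation takes one region at one visit (30 subjects), with arms filled as if by chance.

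**2. Severity imbalance to expect.** The SD of the difference between two arm means is SD x sqrt(2/6). Simulation with 200,000 draws per mix gives:

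| Assumed CR-PCSS mix 2/3/4 (%) | SD | SD of two-arm difference | Mean highest-to-lowest gap, 5 arms | Gap at least 0.5 level | Gap at least 1 level |
|---|---|---|---|---|---|
| equal thirds | 0.82 | 0.47 | 0.77 | 90% | 29% |
| 10/45/45 | 0.65 | 0.38 | 0.61 | 80% | 10% |
| 20/60/20 | 0.63 | 0.37 | 0.59 | 77% | 8% |
| 5/80/15 | 0.44 | 0.25 | 0.40 | 42% | 0.3% |

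So the mean gap is about 0.4 to 0.8 level, and its size depends heavily on the mix.

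**3. Bias and coverage without adjustment.** Assume a 25/50/25 mix, Likert SD 0.9 and no true arm effect, with 20,000 simulated regions at each of the correlations 0, 0.3 and 0.5. The unadjusted contrast averages 0 and its 95% CI covers about 95% at all three.

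**4. Effect on precision.** The unadjusted SE of a pairwise contrast is 0.9 x sqrt(2/6) = 0.52. With 25 df the half-width is 2.060 x 0.52 = 1.07. One covariate leaves 24 df (t = 2.064). The expected ratio of adjusted to unadjusted half-width is approximately

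sqrt[(1 - r^2) x (1 + 1/23)] x 2.064/2.060

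| Correlation r | Change in half-width |
|---|---|
| 0 | +2% |
| 0.2 | about 0% |
| 0.3 | -2% |
| 0.5 | -11% |
| 0.6 | -18% |

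Simulation at 0, 0.3 and 0.5 agrees to within rounding. The ratio does not depend on the assumed SD.

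**5. Effect on the apparent ranking of arms.** In the step 3 runs, the mean highest-to-lowest gap in arm Likert means is 0.85 unadjusted against 0.83 adjusted at r = 0.3, and 0.85 against 0.75 at r = 0.5. Adjustment therefore removes about 0.02 to 0.10 points. At r = 0 it adds about 0.01 to 0.02.

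**6. When an imbalance has occurred.** Take equal thirds and Likert SD 0.8, and look only at datasets where one arm exceeds another by at least 0.5 level. The unadjusted contrast is then off by 0.17 points on average at a slope of 0.25 Likert points per level, and by 0.33 at a slope of 0.5. With adjustment the average error is about -0.01 at both slopes. These slopes correspond to correlations of 0.25 x 0.82/0.8 = 0.26 and 0.5 x 0.82/0.8 = 0.51. The unadjusted half-width at this SD is 0.95.

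**The case against.** **A larger bias might be inferred.** With a 25/50/25 mix the mean severity gap is 0.66 level. Slopes of 0.38 to 0.64 Likert points per level (r = 0.3 to 0.5) turn this into 0.25 to 0.42 points, which a reader might set against the 0.52 SE as spurious technique effect. That reading fails. It compares a range over five arms with the SE of one contrast, and the severity component is already part of the ordinary 0.85 spread. Removing it narrows that spread by only 0.02 to 0.10. Under chance allocation it is error that the interval already reflects. Step 6 does not contradict this: errors average out over all allocations but not within a dataset whose imbalance has been observed.

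**CR-PCSS is not the only candidate.** This stands. Screening Hexsel CSS (B) is also a per-area baseline in SAP Table 12. CR-PCSS is still preferable because it grades the whole area over three entry levels, whereas qualifying dimples are limited to Hexsel 2 or 3.

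**The reported quantity may be unaffected.** SAP 7.7.1.1 presents the arm-by-visit interaction effect. If that means pure interaction coefficients, a severity effect constant over visits cancels. One that grows over visits does not cancel, nor does either kind cancel from arm means by visit. The SAP does not say which is meant.

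**One linear term may be too simple.** Mild areas may have little room to improve and severe ones may seldom reach optimal, so the relation could bend. This is a fair limit; 30 subjects per fit leave little room for more terms.

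**The study is exploratory and imbalance will be visible.** Both are true. But SAP 6.1 plans two-sided 0.05 tests with 95% CIs, and the SAP 7.3 table can show an imbalance without correcting for it.

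**Conclusion.** The gap in the plan is real and modest in effect. The blinded Likert comparison ignores a severity measure already collected and derived for each area. Adjustment would chiefly buy precision: a half-width change from +2% to -18% over correlations 0 to 0.6, material only from about 0.5. It would also correct measured severity imbalance, including any produced by sequential assignment. How much imbalance sequential assignment would add is not quantified here, since the calculations assume chance allocation.

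The documents do not support saying that the unadjusted analysis is biased under chance allocation, or that adjustment would repair sequential assignment: it cannot remove bias from factors not measured. With 6 per arm, random error remains larger than the likely severity shift. All sizes rest on the assumed SD, severity mix and correlation, none of which the documents give.

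**What to change.** - In the SAP 7.7.1.1 Likert model, add the Screening CR-PCSS of the same treatment area as one linear covariate. For the averaged response, use the left-right mean.
- Report adjusted arm means and between-arm contrasts by visit, so that the meaning of the interaction output is clear.
- Amend SAP 6.2 to name the covariate, and keep the unadjusted result as a supportive table.

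No new data are needed. The cost is one model term, short SAP edits and 1 degree of freedom, with intervals about 2% wider if severity proves unrelated to the Likert score.

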17. STATISTICAL CONSIDERATIONS AND METHODS

17.1. Determination of Sample Size

No sample size estimation was done for this study.

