## **2. STUDY OBJECTIVES**

### **2.1. Primary Objective**

The primary objective of this study is to assess the treatment effects of CCH when administered by different injection techniques in subjects with EFP.

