### 3.6.1. Determination of Sample Size

A sample size of 60 subjects (30 with two eligible buttocks and 30 with two eligible thighs) was chosen empirically based on the pragmatic criteria and published data of previous studies.

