**6. STATISTICAL METHODS**

**6.1. General Methodology**

All statistical tests, summary tables and data listings will be prepared using SAS version 9.4

All statistical tests of efficacy parameters will be two-sided with a significance level of  $\alpha=0.05$ , unless specified otherwise. Statistical tests will be supported by presenting estimates and 95% confidence intervals (CI) for the respective treatment effects. These estimates and CI will be based on the linear regression model.

Continuous data will be summarized using descriptive statistics. Discrete data will be summarized using frequency counts and percentages. The denominator will be based on the number of subjects in the appropriate population.

For the purpose of display, the summary results will be rounded as follows:

- Minimum and maximum: same number of decimal places as the raw data.
- Mean and Median: one more decimal place than the raw data.
- SD: Two more decimal places than the raw data.
- Percentages will be displayed with one decimal place precision. A zero count will be left blank.
- The standard form of a percentage change variable is 0 decimal place.

For categorical variables with missing values, a category documenting the frequency of missing values will be displayed in the summary tables.

Summary tables, subject listings, graphs and any supportive SAS output will include footnotes that will indicate:

- Date of data extraction
- Date and time of output generation
- SAS program name, including the path, that generated the output

When calculating percentages, the denominator will be based on the number of subjects with non-missing values. If the denominator is expected to change over time, then the denominator used to calculate the percentage will be based on the number of subjects with non-missing values at each visit. Any subject removed from an analysis will be noted at the bottom of the table along with the reason the subject was removed.

Empty summary tables will be presented with a note stating that “No Subjects Met Criteria.”

Subject listings of all data from the eCRFs as well as any derived variables will be presented.

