## **7.7. Efficacy Analyses**

Efficacy parameters will be summarized and analyzed for each treatment area by treatment arm using the Evaluable Population.

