## **7.8. Safety Analyses**

Safety data will be summarized by treatment arm and by treatment region (ie, Buttocks, Thighs, and Overall) using the Safety Population.

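### The SAP plans no efficacy model across buttocks and thighs, so no efficacy contrast between techniques uses more than 6 subjects per arm although 12 per technique are planned; add one combined model beside the regional ones

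*SAP*

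**What the plan says.** SAP 7.7 sets the level of every efficacy analysis: "Efficacy parameters will be summarized and analyzed for each treatment area by treatment arm using the Evaluable Population". SAP 7.7.1.1 fits a linear mixed model with arm, visit and arm-by-visit as fixed effects. On the level of fitting it says: "This model will be fitted using the response for each treatment area (ie, left buttock, right buttock, left thigh, and right thigh"), followed by the left/right average for buttocks and for thighs. That makes six fits for the Likert score, none with a region term and none spanning the regions. SAP 7.7.2 applies the same model to dimple volume and depth, and 7.7.3 applies it to the Hexsel score.

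Other parts of the plan do combine the regions. For safety: "Safety data will be summarized by treatment arm and by treatment region (ie, Buttocks, Thighs, and Overall) using the Safety Population". The same three-way layout (buttocks, thighs, overall) appears for analysis populations (7.1), demographics (7.3), EFP history (7.5) and medications (7.6).

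The primary objective is to "assess the treatment effects of CCH when administered by different injection techniques in subjects with EFP", with no region named. The allocation is "ie, 6 subjects per region per treatment arm" (SAP 3.1), and no subject is treated in both regions. Protocol 17.5 defines the Likert and dimple endpoints by treatment area and gives a mixed model without saying whether it is fitted by region. SAP Table 13 discloses the per-area fitting as a clarification and gives no reason for having no combined fit.

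**The concern.** The study asks whether five injection techniques differ in effect. Each is given to 6 buttock subjects and 6 thigh subjects, who are different people, with the same planned dose, volume and aliquots in both regions and the same Likert and Hexsel scales. The SAP answers the question separately in each half of the sample and has no pre-specified way to bring the halves together.

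Two things are at stake. The first is precision: intervals for arm differences are wider than the planned sample allows if technique effects are similar across regions. The second is interpretation: with 6 per arm, the two regions will often point to different techniques by chance alone. The plan contains no estimate of arm-by-region differences that would help a reader judge whether such a conflict is real.

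**Working it through.** **Inputs from the documents.** Five arms, 6 subjects per arm per region (SAP 3.1 and Table 2). "All statistical tests of efficacy parameters will be two-sided with a significance level of" 0.05 (SAP 6.1). No SD, effect size or power is given: "No sample size estimation was done for this study" (Protocol 17.1), and "A sample size of 60 subjects (30 with two eligible buttocks and 30 with two eligible thighs) was chosen empirically" (SAP 3.6.1). Discontinued subjects are not replaced, so 6 is a maximum.

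**The plan's own figure.** 5 arms × 6 = 30 per region; 30 × 2 = 60 in total; 6 + 6 = 12 per technique. This agrees with the documents.

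**Assumptions.** One visit, complete data, left/right average as response, and a common SD across arms and regions. Results are in SD units because the documents give no SD.

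**CI half-width for a difference between two arms:** t(0.975, df) × SD × √(2/n).

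- Within a region: n = 6, df = 30 − 5 = 25. 2.060 × √(2/6) = 2.060 × 0.577 = 1.19 SD.
- Combined, with a region term: n = 12, df = 60 − 5 − 1 = 54. 2.005 × √(2/12) = 2.005 × 0.408 = 0.82 SD.
- Combined, with arm-by-region added: df = 60 − 10 = 50, still 0.82 SD.
- Ratio 0.818/1.189 = 0.688, so 31% narrower.

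In Likert points (scale −1 to 3), for an assumed range of SD:

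| Assumed SD | Within region | Combined |
|---|---|---|
| 0.6 | 0.71 | 0.49 |
| 0.8 | 0.95 | 0.65 |
| 1.0 | 1.19 | 0.82 |
| 1.2 | 1.43 | 0.98 |

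**Detectable difference** (80% power, two-sided 0.05, noncentral t, no multiplicity adjustment): 1.68 SD within a region, 1.17 SD combined. Power for a 1.0 SD difference: 38% and 67%.

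**Chance that the truly better technique ranks first.** Simulated sets of five arm means, each with standard error SD/√n. One technique is better by the stated amount and the other four are equal. When the advantage exists in one region only, the combined contrast sees half of it.

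| True advantage | One region's model (n = 6) | Combined, same advantage in both regions (n = 12) | Combined, advantage in one region only |
|---|---|---|---|
| 0.3 SD | 41% | 51% | 34% |
| 0.5 SD | 57% | 72% | 45% |
| 0.8 SD | 78% | 92% | 62% |

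With 0.5 SD in one region and 25% of that in the other, the combined analysis ranks the technique first 52% of the time; with 50% of it, 59%. The break-even against 57% therefore lies where the other region shows somewhat under half the effect.

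**Agreement between regions.** If one technique is 0.5 SD better in both regions, the two regional analyses name the same top technique only 37% of the time.

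**Overstatement of the apparent best when all five are equal.** The expected maximum of five standard normals is 1.163. Divided by √6 this is 0.47 SD; divided by √12 it is 0.34 SD.

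**The case against.** The case for the plan as written is substantial.

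- **The design is regional.** Protocol 10.3 sets five arms per region, and Protocol 17.5 states the Likert and dimple endpoints by treatment area. The split is therefore not an error or a hidden departure, and Table 13 discloses it. This stands, and the regional models should stay.
- **Equal technique differences across regions are not established.** The thigh severity scale describes undulations and protuberances, the buttock scale dimples. Region is not randomised, since subjects eligible in both go to thighs. A shared Likert scale does not make the regions interchangeable. This stands too. A reader might infer that pooling is free and should become the lead analysis. The one-region-only results above show a real loss, so the documents do not support that.
- **The side-specific models have a use.** A reader might call them redundant because both sides get the same technique. But Protocol 12.5 and SAP 3.6 let a dimple-free side go untreated on Day 22 or 43 while the other side is treated, so exposure can differ by side. They should not be dropped.
- **Safety is already combined.** It would be wrong to say that every technique comparison rests on 6 per arm. SAP 7.8 has an overall summary for safety. The point is confined to efficacy.
- **Little is lost, because the study is exploratory.** With exact 6 + 6 balance, the combined contrast is essentially the mean of the two regional contrasts. There is no power target to miss, and even 12 per arm detects only about 1.17 SD. This limits the weight of the point. It does not supply the missing pre-specified combined interval or the arm-by-region estimates.

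The table shells are in SAP Module 2, which is not part of the reviewed text, so a combined display there cannot be excluded.

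**Conclusion.** The point holds for efficacy. As written, the SAP specifies no efficacy contrast between techniques that uses more than 6 subjects per arm, against 12 planned per technique and an objective that names no region. The cost is wider intervals and less reliable ranking, of the size shown above, provided that technique differences are similar in the two regions and the assumptions of equal SD and complete data hold roughly. If the advantage is confined to one region, the regional model is the better guide. The gap is therefore the absence of a combined analysis, not the presence of regional ones. It is an inexpensive improvement to an exploratory plan. It does not show that the planned models are wrong or that a sample-size claim has failed.

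**What to change.** In SAP 7.7.1.1, and by reference in 7.7.2 and 7.7.3, keep the side-specific and within-region average models. For each modelled endpoint, add one model on all Evaluable subjects:

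- response: the left/right average;
- fixed effects: arm, visit, arm-by-visit, region and region-by-visit;
- subject as the repeated unit;
- output: arm means and arm differences with 95% CIs at each visit, with arm-by-region estimates shown beside them.

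State in the SAP that the combined contrast averages over any technique-by-region difference, and that it is read together with the regional results and does not replace them. Record the addition in Table 13.

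The cost is SAP wording and one further model and table per endpoint, with no new data or procedures. The statistical price is the averaging just described. Check timing first: the protocol synopsis estimated the last subject's completion for January 2019 and SAP version 2.0 is dated 11 February 2019. If the efficacy data have already been analysed, label the combined model post hoc.
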